Historic MCI control subjects will be identified from the Derwent Memory Clinic data base which contains data on more than 400 MCI patients. These controls will be used in the analyses for comparison of outcomes in treated and untreated patients. Controls will be matched on the following criteria:

- age
- gender
- MMSE score
- education

A placebo social contact control group will not be included as previous studies indicate no difference between social-contact and no-contact control groups on cognitive or functional measures [Willis, Tennstedt, Marsiske, Ball, Elias, Koepke, Morris, Rebok, Unverzagt, Stoddard, and Wright 2006;Willis *et al.* 1983;Clark *et al.* 1997].

Clinical assessment

The standard clinical workup includes a detailed history of cognitive impairment from the patient and an informant, a full psychiatric history, a mental state examination, a physical examination with an emphasis on neurological examination and a neuropsychological test battery. Measures/tests included are:

- National Adult Reading Test (NART) [Nelson 1991]
- The Mini-Mental state examination (MMSE) [Folstein et al. 1975]

- Cambridge Cognitive Examination (CAMCOG-R) [Huppert et al. 1995]
- Logical Memory Test [Wechsler 1997]
- Halstead Trail Making test (TMT) [Davies 1968]
- The Clinical Dementia Rating (CDR) [Berl 1988]
- Clifton assessment procedure for the elderly, Behavioural rating scale only (CAPE) [Pattie and Gilleard 1979]
- 15 item Geriatric Depression Scale (GDS-15) [Yesavage *et al.* 1982]

Trail design

We plan a longitudinal study where participants will serve as their own controls. Participants will start with **phase one** during which they will engage in 12 weeks DSD program designed to increase behavioural flexibility and therefore adherence with the planned physical, cognitive and social interventions in phase two. This will be followed by **phase two** during which they will take part in a 12 weeks physical, cognitive and social activity program. Outcome measures will therefore be collected at three time-points: baseline (Time 1), midway, week 12 (Time 2) and following phase 2 (Time 3).

Outcome measures

The main outcome is the development and implementation of the multimodal intervention program. Success will be measured as participant compliance during the program (% of participants compliant with intervention program), feedback on the interventions and continued engagement after completion.

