Quality of life will be measured on the World Health Organization Quality of Life (WHOQOL) – BREF and change in every day activities on the Alzheimers' Disease Cooperative Study MCI Activities of Daily Living Scale (ADCS-MCI-ADL)[Galasko *et al.* 1997].

4. Measure of brain activation /perfusion with near infrared spectroscopy heamoenephalography (NIRS-HEG)

We will collect brain activation data from all participants at the three time points during administration of the divided attention paradigm which runs for 5 minutes.

We will use a CE marked Oxymon Mk (Artinis, Netherlans) to measure changes in light attenuation at four discrete wavelengths (775,825,,850 and 905 nm) using four laser diodes as light sources and photon multiplier tube as detector. Sensors will be placed over the left prefrontal (F3), the superior parietal (P3) and the occipital cortex (O1) and the right frontal pole (Fp2), according to the international 10-10 system developed for EEG. This portable system does not involve any ionising radiation.

Treatment sessions

1. Physical exercise

Participants will be asked to complete 36 training sessions at a frequency of two to three per week. Half of all the groups (Feedback participants, **FP-group**) will be randomly allocated sound and vibration feedback to help them to stay in a predetermined training zone. Heart rate for the moderate training zone (less than 60% of VO2 max; 65-77% of maximum heart rate) will be determined for each participant from their predicted maximum heart rate (HR max = 220 – age). The other groups will not receive feedback but heart rate will still be measured (Monitoring participants, **MP-group**); this group will receive instruction on utilising subjective reports of effort to guide their optimal level of effort. Assignment to FP-group and MP-group will alternate so equal numbers are obtained for statistical comparison. In addition each participant will be issued

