with a large poster providing visual instructions of how to use the equipment and do a 10 minute warm-up routine (Appendix B). They will receive home visits and supervision at sessions 1, 3, 8, 14 and 20 (see Appendix C for a timelines). They will also receive regular weekly telephone contact to provide support and monitor progress. Heart rate monitors (Oregon Scientific SE102I) measure electrocardiographic signals via a chest strap. Heart rate zones are programmed into the monitors and auditory signals and vibration of the monitor attached to the arm provides feedback and alerts the patient when heart rate is outside the preset parameters. Heart rate monitors will be programmed by the research team. An electronic data logger (Oregon Scientific WM100) which collects continuous data from the chest strap will be activated during activity so that heart rate data during physical activity is captured for later analysis.

Patients taking beta blocker medication will exercise at a heart rate equivalent to a specific effort (14 on the Borg scale) as these medications lower heart rate and result in sub optimum training when training zones are calculated as described above [Tabet *et al.* 2008;Borg 1970]. The relevant rate will be determined during the initial supervised walking sessions.

2. Cognitive training

In addition to Physical exercise participants will be asked to complete 12 cognitive training sessions at a frequency of 1-2 per week. Training will take place on an individual and group basis, both supervised and unsupervised. The duration of training sessions will vary from 30 to 90 minutes depending on the type of training. A variety of training techniques will be employed with the aim to improve specific cognitive components such as attention, speed of processing, working memory, problem solving and reasoning. For training we will use the program developed by Lumosity (www.lumosity.com). Centre-group participants will have access to online resources either at training centres provided and staffed by the Adult Community Learning (ACL) Service in Essex, or at home. Online-group participants will be provided with access to computers and the internet for the duration of the study. These participants will not require any existing computing skills as all content will be accessed and supervised remotely by the researchers and ACL staff. Participation on the cognitive Lumosity program will be anonymised and data will be collected on the time and duration

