Each new group of participants will receive an introductory talk from an expert patient who has already undergone the training. The high level of similarity of the expert patient and recruited participants will provide social proof of the anticipated success of planned activities. Participants will be informed that the 12 week wait before they start the program will be due to the popularity of the study. This will encourage herding which could enhance engagement due to perceived scarcity of opportunity. Participants will be informed of the cash value of the treatment they will receive (reciprocity). Participants will be made aware of the expertise of all the involved researchers (authority) and the researchers will receive specific instruction to makes them more likeable to participants. This will include instructions to encourage desirable or successful behaviour in the group setting whilst dealing with difficulties arising from training on an individual basis. Choices related to any part of the interventions will be kept to the minimum as increased choice is strongly associated with decreased engagement. The "fear message" which is the high risk of developing dementia in this study population will be accompanied by specific information on potential ways of reducing the risk in order to avoid future recruits from "blocking out" the message with problematic behaviour.

Implementation of DSD program during preparatory phase

Participants will be asked to complete DSD activities in order to increase their behavioural flexibility for the second phase of the program. They will complete a different DSD task everyday of the week for four weeks of the last 12-weeks of the control period (7 tasks a week x 4 weeks= 28 tasks). Tasks are not to be repeated and in order to provide some choice we provide a list of 36 tasks, which will enable participants to aviid some activities. They will do each activity once and then record the date, location any comments and assign a mark on a 4 point like-dislike scale (I enjoyed doing this activity: I agree strongly/agree/disagree/disagree strongly). This record will serve as a reminder that the activity has already been completed and will also aid in memorising the episode. The list of activities is listed in Appendix A

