2. We would also like to measure the effects of the DSD on behavioural flexibility in the mild cognitive impairment patient group in order to see if the intervention alters behaviour flexibility and if this correlates with the primary or secondary outcome measures, thereby allowing us to determine the effectivety of the DSD program. We plan to measure behavioural flexibility with an informant completed rating scale (FIT-720) consisting of 15 items which should take no longer than 5 minutes to complete. The FIT-720 is a standardised tool for assessing the gap between how a person sees their behaviours and how they are perceived by others. The questionnaire is completed by someone close to the participant who would be able to observe changes in behaviour. Please see version 1: dated 22nd January 2010.

Information technology resources

Online-group participants will be issued with personal computers (iMac 24 inch, Apple Computer) and a broadband internet connection (Business Broadband NET connection) activated over existing British Telecoms lines. The computers will be password protected and secured with a safety cable. Participants will be contacted by telephone prior to video teleconferencing sessions and will then agree to receive the call, thereby protecting privacy. Computers will be set up so that only named research staff will be able to connect remotely and facilitate use. Participants will not have free access to use the computers outside the programmed activities. Access to all other resources on the internet will be blocked but may be accessed if necessary by research staff during supervised sessions, particularly during the social activities. No personal information will be used or stored on the computers. The computers will be placed and removed by research staff. The internet connection and computer will be provided at no cost to participants for the 12 weeks of their participation in phase 2.

Centre group participants will have supervised access to computers at ACL centres provided under existing safety regulations and data protection policies.

Expected adverse events

The following adverse events are associated with the planned activities:

Physical training related

Overexertion Headache Sore / painful muscles Chest pain

Low abdominal pain

Sprain

Strain

Muscle cramps

Fatigue

Blisters, soft tissue injury

Breathlessness

Exertional dyspnoea

Elevation of BP

Irregular heart beat

Palpitations

Nausea

Dizziness

Falls

Sunburn

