Feeling very hot and perspiring profusely

Dehydration

Getting lost

Confusion

Wandering

Lack of coordination

Increased recovery time

Cognitive activity related

Headache Fatigue Wrist pain/strain from using mouse

Eye strain

Social activity related

Feelings of frustration Social anxiety

Ethical approval

Ethical approval will be sought for the study from the local research ethics committee.

Statistical analysis

Subjects will serve as their own controls and data will be captured at baseline, following 12 weeks of DSD and at the end of phase two (study week 26). Continuous variables will be compared using paired t-tests and analyses of variance. All statistics will be analysed using SPSS / PC+ version 10.0 (Statistical Package for Social Sciences).

Sample Size.

The planned sample size (n=128) will enable us to detect a change of 0.25 standard deviations in the performance outcomes (details here) with 80% power at the 5% level of significance. The planned comparison between the community based /centre based groups (n=64) will enable us to detect a 0.5SD difference with 80% power at 5% significance. In this feasibility study, it is unlikely that this scale of change will be observed. More important will be our ability to estimate the potential size of the changes. In this case, with 128 subjects we can estimate the change to within +/- 17.5%SD (i.e. the width of the 95% CI will be 35%SD).

Analysis

The principle analysis will focus on the estimation of the change resulting from the intervention. This will be estimated by mean change and 95% CI. Supplementary analyses will employ Repeated Measures ANOVA to examine the changes from Baseline, start of therapy to the end of therapy. These analyses will be extended to assess the role of background covariates, such as age, sex health status etc. Abbott RD, White LR, Ross GW, Masaki KH, Curb JD, Petrovitch H. Walking and dementia in physically capable elderly men. JAMA 2004; 292: 1447-1453.

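### The FIT-720 analysis is said to determine whether the DSD programme is effective, but no described group gives a DSD-free FIT-720 comparison; the DSD exposure is also labelled inconsistently (minor)

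*Protocol*

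**What the plan says.** **The FIT-720 analysis.** At the end of the DSD implementation section the protocol adds a measure of behavioural flexibility, the FIT-720, a 15-item scale completed by someone close to the participant. Its purpose is "in order to see if the intervention alters behaviour flexibility and if this correlates with the primary or secondary outcome measures", and the conclusion drawn is "thereby allowing us to determine the effectivety of the DSD program".

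**Who receives DSD.** Under Trail design, all participants start with phase one, "during which they will engage in 12 weeks DSD program designed to increase behavioural flexibility". Participants act as their own controls, with assessments at Time 1 (baseline), Time 2 (week 12) and Time 3 (after phase two).

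**How much DSD.** Statistical analysis agrees with Trail design on duration: "data will be captured at baseline, following 12 weeks of DSD". The section on implementing DSD is more specific: "They will complete a different DSD task everyday of the week for four weeks of the last 12-weeks of the control period". It gives the total as 28 tasks and adds: "Tasks are not to be repeated and in order to provide some choice we provide a list of 36 tasks".

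**The concern.** A statement that a programme is effective needs a contrast with what would have happened without it. When everyone receives the programme and the instrument is used only in those people, a change in score cannot be credited to the programme. A correlation between that change and an outcome does not supply the missing contrast, because both may follow from something else.

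Taken at its word, the protocol would lead to a report that DSD works, or does not, resting on uncontrolled change. DSD is included because it is expected to raise adherence, and compliance is one of the measures of success for the main outcome. A future randomised trial is among the study's purposes, so an unsupported verdict on DSD could decide whether it is carried forward.

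The exposure labels matter less, but they bear on the same sentence of a future report. A reader of Trail design or Statistical analysis would describe three times the DSD duration that the implementation section schedules. The control-period label could also suggest that Time 1 to Time 2 is an untreated reference.

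**Working it through.** **Step 1. Look for a DSD-free FIT-720 comparison.** Each contrast that the protocol describes is taken in turn.

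- *Feedback versus monitoring groups* (Treatment sessions, Physical exercise). Half the groups "will be randomly allocated sound and vibration feedback to help them to stay in a predetermined training zone"; the others are monitored without feedback. The difference lies in phase-two exercise, and both sides have already had DSD.
- *Centre versus online groups* (Cognitive training; Information technology resources; Sample Size). "Online-group participants will be provided with access to computers and the internet for the duration of the study"; the information technology section ties this provision to the 12 weeks of phase two. The difference is in how phase two is delivered, and both sides have had DSD.
- *Historic controls* (Historic MCI control subjects; Clinical assessment). These patients did not take part in DSD, but they are drawn from the clinic database. The workup lists eight measures: NART, MMSE, CAMCOG-R, Logical Memory, Trail Making, CDR, CAPE behavioural rating and GDS-15. The FIT-720 is not among them. A comparison made after phase two would in any case combine DSD with the exercise, cognitive and social programme.
- *Participants as their own controls.* Time 1 to Time 2 contains DSD. Time 2 to Time 3 follows DSD and contains the whole phase-two programme. Neither interval is a DSD-free reference.

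A placebo social-contact group is expressly left out. Count of DSD-free FIT-720 comparators: 0 of the three groupings, and none within person.

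**Step 2. Does the correlation help?** All participants are exposed, so the correlation relates FIT-720 change to outcome among treated people only. The protocol itself describes motivation as the best indicator of adherence to exercise, and motivation could drive both quantities. Motivating adherence also describes persuasion techniques, one of which concerns how the 12-week wait is explained to participants. Before-after change cannot separate these from DSD.

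**Step 3. Is this a matter of numbers?** No. The protocol's own sample size reproduces for a paired comparison at two-sided 5% (two-sided is my assumption):

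- n = ((1.960 + 0.842) / 0.25)² ≈ 126 by the normal formula; the noncentral t gives 128, with power 0.802.
- 95% half-width = 1.979 / √128 = 0.175 SD, as stated.

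Precision does not identify a cause. As an illustration with assumed values only, suppose DSD has no effect, FIT-720 drifts for other reasons by d SD of the change score, and all 128 participants contribute. The paired t-test has noncentrality d√128 and is significant with these probabilities:

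| Assumed drift d | 0.10 | 0.15 | 0.20 | 0.25 | 0.30 |
|---|---|---|---|---|---|
| P(significant) | 20% | 39% | 61% | 80% | 92% |

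The protocol gives no figure for such drift, so this range is not an estimate of bias.

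**Step 4. Set the exposure labels side by side.**

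- Trail design and Statistical analysis: 12 weeks of DSD.
- Implementation section: 7 tasks a week × 4 weeks = 28 tasks, drawn from 36 without repetition (36 − 28 = 8 spare).
- Ratio of the labelled durations: 12 / 4 = 3. The scheduled tasks occupy 4 / 12 = 33% of a 12-week phase.
- The implementation section's heading refers to a preparatory phase, but its text calls the same interval a control period.

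**The case against.** The strongest defence is that the uncontrolled design is openly declared. This is a feasibility study, the randomised trial is left for later, and the principal analysis is estimation of mean change with a confidence interval. The FIT-720 is introduced as something the investigators would also like to measure; it is neither a study aim nor a listed outcome, and no test or decision rule hangs on it. What would actually be done, namely describing change and correlating it, is close to what the fix proposes. All of that stands, and it limits the weight of the point. It does not supply a DSD-free contrast, and the clause still draws a conclusion that the analysis cannot reach.

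On exposure, the defence is largely right. The implementation section is the operational text. It places four active weeks within a 12-week period and shows its arithmetic, so the other two sections can be read as naming the phase by its content. A reader might infer that daily tasks were meant for all 12 weeks and that the task list is too short. No section prescribes that schedule, and the list is sufficient for the four weeks that are prescribed. Nor is it a fault that the particular four weeks are not named in the text available, since the appendix of timelines was not available to check.

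A reader might also infer that the protocol treats Time 1 to Time 2 as an untreated control interval. It does not say so: both Trail design and Statistical analysis put DSD before Time 2. The phrase control period is a loose label that invites that reading.

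**Conclusion.** The point holds for the effectiveness claim. With DSD given to everyone and no DSD-free FIT-720 data described, the study can report before-after change in FIT-720 and its association with compliance and outcomes, and nothing stronger. This assumes that the FIT-720 is used only in study participants. The protocol does not say whether the clinic database holds it, but the listed workup gives no sign that it does.

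The inconsistent exposure labels (12 weeks against four weeks and 28 tasks) and the control-period label are real but editorial. The intended schedule can be recovered from the text.

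The matter is peripheral to the trial. The sample size of 128, the stated precision and the compliance outcome do not change, and no size of bias is claimed. It should still be corrected, because it governs what the study may conclude about DSD.

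**What to change.** 1. In the FIT-720 paragraph, replace the effectiveness clause with: *exploratory description of change in FIT-720 and its association with compliance and outcomes; the effect of DSD cannot be estimated in this design*.
2. In Trail design and Statistical analysis, describe phase one as *a 12-week preparatory phase that includes four weeks of daily DSD tasks*.
3. In the implementation section, replace the control-period label with *preparatory phase*, and note that the Time 1 to Time 2 change includes DSD.

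Cost: protocol wording only. No new data, participants or analyses are needed.

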- To prospectively follow MCI patients to monitor the rate of conversion to dementia and to compare rate of conversion to historic controls.

Methods

Subjects

MCI Subjects

We plan to recruit 128 patients diagnosed with MCI (amnestic and non-amnestic) from the Derwent Memory Clinic at St Margaret's and Princess Alexandra Hospitals, Essex, UK. The general practitioner of all subjects will be informed of their participation in the study.

Inclusion criteria for patients with MCI

- Patients fulfilling criteria for AMCI [Petersen, Doody, Kurz, Mohs, Morris, Rabins, Ritchie, Rossor, Thal, and Winblad 2001]:
 - i. Memory impairment for age and education
 - ii. No impairment in other cognitive domains
 - iii. Normal social activities
 - iv. Patient is not demented
- 2. Patients diagnosed with other subtypes of MCI (cognitive impairment in one or more non-memory domain)
- Sedentary lifestyle with no regular participation in physical exercise defined as two or three times a week for at least 20 minutes duration, or participation in active organised sport more than once a week, in the previous six months.
- 4. Willing and able to give informed consent.
- 5. Availability and access to safe exercise environments, such as paths or roads with sidewalks for walking or cycling.
- At low risk from serious adverse effects from increased physical activity as indicated by performance on the revised Physical activity readiness questionnaire (PAR-Q).

Exclusion criteria for patients with MCI

- 1. Type 1 (insulin dependent) diabetes mellitus.
- 2. Blood pressure above 160/100 mmHg.
- 3. Body weight more than 140% of ideal body weight.
- 4. Musculoskeletal or other medical problems preventing safe participation in regular moderate intensity exercise (65-77% of predicted maximum heart rate). This will include a resting tachycardia (heart rate above 100 bpm) and history of myocardial infarction or unstable angina within the last month.

Participants with modifiable exclusion criteria will be reconsidered after successful management. Patients will be referred for medical /cardiological review and management prior to commencing exercise if indicated by the PAR-Q and the intervention will be guided by the PARmed-X.

Participants taking medications affecting heart rate will need to be on a stable dosing regime for 3 months prior to commencing in order to control for potential spurious results on fitness measures caused by these treatments.

Historic MCI control subjects

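### The stated power and precision need complete paired data from all 128 people recruited, with no allowance for loss over 26 weeks

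*Protocol*

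**What the plan says.** The Subjects section of the Protocol sets the recruitment target: "We plan to recruit 128 patients diagnosed with MCI". The Sample Size paragraph then makes three claims on that number:

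- Within-person change: "The planned sample size (n=128) will enable us to detect a change of 0.25 standard deviations", "with 80% power at the 5% level of significance".
- Comparison of the two delivery groups, 64 in each: "n=64) will enable us to detect a 0.5SD difference with 80% power at 5% significance".
- Precision: "with 128 subjects we can estimate the change to within +/- 17.5%SD".

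Of the change due to the intervention, the Analysis paragraph says: "This will be estimated by mean change and 95% CI". Paired t-tests and analyses of variance are named for continuous variables, and a second layer follows: "Supplementary analyses will employ Repeated Measures ANOVA to examine the changes from Baseline, start of therapy to the end of therapy". Assessments are at baseline, after the 12-week preparatory phase and at the end of phase two, which the Statistical analysis section places at study week 26. The Protocol gives no expected loss, no retention figure and no margin between the number recruited and the number analysed.

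**The concern.** A mean change can be calculated only for people seen at both visits being compared. If the number recruited equals the number the power statement needs, that statement assumes that nobody misses either visit. The Protocol gives no ground for that assumption. It enrols sedentary people with mild cognitive impairment, asks for 36 exercise and 12 cognitive sessions after a 12-week preparatory phase, and counts the percentage compliant among its success measures. Stopping the programme is not the same as missing an assessment, but some missed assessments over six months are likely.

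At stake is whether the study can deliver the precision it promises. The Study Aims include setting the sample size of a later randomised trial. The width of the interval around the observed change therefore feeds directly into that decision.

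**Working it through.** **Inputs.** From the Protocol: 128 recruited; 128 in the power and precision statements; 0.25 SD; 80% power; 5% significance; 64 per group and 0.5 SD for the group comparison; half-width 0.175 SD. Assumed: a two-sided test (sidedness is not stated, but a one-sided 5% test would give 87.9% power at 128, so two-sided is what reproduces); SD read as the SD of the change in the paired calculation; and loss rates of 10, 20 and 30%, because the documents give none.

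**Step 1. Reproduce the stated figures.**

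- Normal approximation: n = ((1.960 + 0.842) / 0.25)² = 125.6, so 126.
- Exact noncentral t, n − 1 degrees of freedom and noncentrality 0.25√n: the smallest n with at least 80% power is 128, with power 80.15%.
- Half-width = t(0.975, 127) / √128 = 1.979 / 11.314 = 0.1749 SD, against the stated 0.175.
- Two groups, exact t, noncentrality 0.5√(n/2): the smallest n is 64 per group, with power 80.1%.

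All three claims are arithmetically correct with complete data on 128.

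**Step 2. Look for slack.** At n = 127, power is 79.8% and the half-width is 1.979 / 11.269 = 0.1756 SD. By the exact calculation there is no margin; by the normal approximation there is a margin of two people (126 against 128).

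**Step 3. Apply a range of losses.** Number analysed = 128 × (1 − loss) and number per group = 64 × (1 − loss), both rounded down. Half-width = t(0.975, n − 1) / √n. The detectable change is the effect at which exact power is 80%.

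| Assumed loss | Analysed | Power at 0.25 SD | Detectable change | 95% CI half-width | Per group | Power at 0.5 SD |
|---|---|---|---|---|---|---|
| 0% | 128 | 80.2% | 0.25 SD | 0.175 SD | 64 | 80.1% |
| 10% | 115 | 75.8% | 0.26 SD | 0.185 SD | 57 | 75.4% |
| 20% | 102 | 70.6% | 0.28 SD | 0.196 SD | 51 | 70.6% |
| 30% | 89 | 64.5% | 0.30 SD | 0.211 SD | 44 | 64.0% |

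With 51 per group, the between-group difference detectable with 80% power is 0.56 SD.

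**Step 4. Who each named method uses.** A paired t-test or mean change needs the two visits being compared, so someone who misses only week 12 still counts in baseline against end of phase two. A standard Repeated Measures ANOVA over the three time points needs all three visits, so that person is lost from it. The supplementary analysis can therefore rest on fewer people than the principal one.

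**The case against.** The best defence is that this is a feasibility study. Its main outcome is the development and implementation of the programme, judged by compliance, feedback and continued engagement; fitness, cognition and quality of life are secondary. The Sample Size paragraph itself says that changes of this size are unlikely to be seen and that estimation matters more than power. On precision the loss is modest: 10% attrition moves the half-width from 0.175 to 0.185 SD. The Protocol also supports adherence with a preparatory phase, home visits and weekly telephone calls. All of this stands and limits the importance of the point. It does not remove it, because the preferred precision claim also needs all 128.

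Missing-data rules and analysis populations may sit in a statistical analysis plan that is not shown, so their absence is not raised here. The point concerns what the Protocol does fix: the recruitment target, the figures attached to it and the named methods.

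A reader might infer three stronger things, none of which the documents support:

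- That paired t-tests discard anyone with a missed visit. They discard only people missing one of the two visits compared. The three-visit requirement belongs to the Repeated Measures ANOVA, which is labelled supplementary.
- That people who stop exercising are taken out of the analysis. Nothing in the Protocol says so. Compliance is reported as a percentage, and brain activation data are planned for every participant at all three time points.
- That the estimated change is biased upward. This is plausible if those who decline or tolerate the programme poorly miss the last visit, but the documents establish neither the direction nor the size of any bias.

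**Conclusion.** The point holds as one of sample-size justification. The stated power, group comparison and interval width are correct only if all 128 people recruited supply complete paired data, and by the exact calculation any loss takes them past the stated values. How far depends on a loss rate that the Protocol does not give. Under assumed losses of 10 to 30%, power for 0.25 SD falls to between 76 and 65% and the interval widens to between +/-18.5 and +/-21.1% SD. That is a moderate shortfall. It does not threaten the feasibility objective, but it makes the Protocol's promised precision too favourable. The calculations assume a two-sided 5% test and, in the group comparison, equal loss in both groups. The default loss of cases in the supplementary Repeated Measures ANOVA is a smaller, related weakness.

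**What to change.** State an expected retention with its basis, and restate the Sample Size paragraph for the number expected to have paired data. At 80% retention, for example, it would read: 102 analysed, a detectable change of 0.28 SD with 80% power, a 95% CI of +/-19.6% SD, and a detectable difference of 0.56 SD between groups of 51. Recruitment can stay at 128. Keeping 128 analysed would instead need 128 / 0.8 = 160 recruited, which a feasibility study hardly warrants.

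Replace the supplementary Repeated Measures ANOVA with a linear mixed model that has visit as a categorical factor and uses every available visit. State that it assumes data missing at random. It recovers information from people with a missed visit, but it does not guarantee removal of bias if people leave because they are declining.

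The cost is a few sentences, a slightly less favourable stated precision and one explicit modelling assumption. No additional participants are needed.
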